## 8 STUDY PARTICIPANTS

### 8.1 Disposition

The number of enrolled participants will be presented in a flow chart by age and randomization group. The number of visits completed and missed will be presented, along with a breakdown of the analysis populations.

### 8.2 Demographics

Demographic information including age, sex, race, ethnicity, and enrollment site will be presented by treatment group. Summary statistics (e.g., mean, standard deviation, median) will be presented for continuous variables. Categorical variables will be described with frequencies and percentages.

Demographics for the ITT population will be presented.

## 9 ANALYSIS OF STUDY OBJECTIVES

### 9.1 Primary Objective

The primary objective will be analyzed using the immunogenicity population. All endpoints will be assessed with two-sided tests and alpha set to 0.05.

*Endpoint i:*

The proportion of participants with a seroprotective HAI before and 28-42 days after immunization will be compared between group i (concomitant administration) and ii (influenza administered first), using the following null ( $H_0$ ) and alternative ( $H_1$ ) hypotheses:

$H_0$ : Simultaneous group – Sequential group = 0

$$H_0: \pi_1 - \pi_2 = 0$$

$$H_1: \pi_1 - \pi_2 \neq 0$$

where  $\pi$  is the seroprotective rate.

P values and confidence intervals for the geometric mean titer ratio will be estimated using a logistic regression adjusted for site.

*Endpoint ii:*

The proportion of participants achieving seroconversion will be compared between group i (concomitant administration) and ii (influenza administered first), using the following null ( $H_0$ ) and alternative ( $H_1$ ) hypotheses:

$H_0$ : Simultaneous group – Sequential group = 0

$$H_0: \pi_1 - \pi_2 = 0$$

$$H_1: \pi_1 - \pi_2 \neq 0$$

where  $\pi$  is the seroconversion rate.

P values and confidence intervals for the geometric mean titer ratio will be estimated using a logistic regression adjusted for site.

*Endpoint iii:*

GMTs before and 28-42 days after immunization will be compared between group i (concomitant administration) and ii (influenza administered first), using the following null ( $H_0$ ) and alternative ( $H_1$ ) hypotheses:

$$H_0: \mu_1 / \mu_2 = 1$$

$$H_1: \mu_1 / \mu_2 \neq 1$$

where  $\mu$  is the geometric mean titer.

P values and confidence intervals for the geometric mean titer ratio will be estimated using a generalized estimating equation linear regression accounting for site clustering.

*Endpoint iv:*

Geometric mean fold rise will be compared between group i (concomitant administration) and ii (influenza administered first), using the following null ( $H_0$ ) and alternative ( $H_1$ ) hypotheses:

$$H_0: \mu_1 / \mu_2 = 1$$

$$H_1: \mu_1 / \mu_2 \neq 1$$

where  $\mu$  is the geometric mean fold rise.

P values and confidence intervals for the geometric mean titer ratio will be estimated using a linear regression adjusted for site.

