Study Duration:	12 months total Enrollment: Aug — Oct 2023 Vaccination: Aug — Nov 2023 Blood draws: Aug 2023 — May 2024 Active surveillance for illness: Aug 2023 — May 2024 Laboratory testing: Nov 2023 — Jul 2024
Participant Duration and Number of Participants:	
 • Up to 10 months (Aug 2023 — May 2024) • 800 total participants (600 aged 18-64 years, 200 aged 6-11 years) at 4 sites (only two sites will enroll children aged 6-11 years)
Randomization:	Adults aged 18-64 years, 2:1:1 permuted block randomization 
 i. Concomitant cclIV4 + COVID-19 mRNA (day 0) [n = 300] ii. Sequential cclIV4 (day 0), COVID-19 mRNA (day 28) [n = 150] iii. Sequential COVID-19 mRNA (day 0), cclIV4 (day 28) [n = 150]

	
Children aged 6-11 years, 2:1:1 permuted block randomization
 
 i. Concomitant ccIV4 + Moderna COVID-19 mRNA (day 0) [n = 100] ii. Sequential ccIV4 (day 0), Moderna COVID-19 mRNA (day 28) [n = 50] iii. Sequential Moderna COVID-19 mRNA (day 0), ccIV4 (day 28) [n = 50]

Description of Study Procedures:
	
This study is a randomized immunogenicity study in an enrolled cohort with active surveillance for acute respiratory illness (ARI). During this study, participants will be randomly assigned to receive an approved quadrivalent influenza vaccine (Flucelvax [ccIV4]) and mRNA COVID-19 vaccine (Moderna) either concomitantly (given in contralateral arms) or sequentially (28 days apart).
 
Blood samples from participants will be collected for measurement of biomarkers of immune response at baseline (visit 1; day 0), post-vaccination 1 (visit 2; day 28), post-vaccination 2 (visit 3; day 56), and post-season (visit 4; day 180). Serum and peripheral blood mononuclear cells (PBMC) and plasma (target to collect PBMC and plasma samples at every visit from a subset of approximately 250 participants; 200 adults and 50 children) samples will be isolated from whole blood and tested for biomarkers of vaccine immunogenicity, and duration of antibody responses.

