	
 vi. Determine influenza HAI and MN antibody titers against circulating influenza viruses during baseline and post-vaccination vii. Determine SARS-CoV-2 antibody binding titers and viral neutralization titers (in a subset of samples) against circulating SARS-CoV-2 variants during baseline and post-vaccination viii. Compare the frequencies of antigen-specific T and B cells utilizing high-dimensional flowcytometric analysis of innate and adaptive immune cell phenotype characterization using fluorochrome-conjugated antigen tags, and intracellular cytokine staining to 2023-24 cclIV4 and mRNA COVID-19 vaccines administered either concomitantly or sequentially, 28 days apart ix. Compare transcriptome, B cell receptor (BCR) and T cell receptor (TCR) diversity of antigen-specific cells and assess serological antibody repertoire (clonotypes) using 10X genomics platform, and liquid chromatography/mass spectroscopy in a subset of participants x. Investigate the waning of antigen-specific B cells and antibody clonotypes in a subset of participants xi. Describe safety of concomitant versus sequential administration of cclIV4 and mRNA COVID-19 vaccination

Outcome Measures:
	
Primary Outcome Measures:
 
 i. The percent seroconversion and seroprotective titer, the geometric mean titer (GMT), and geometric mean fold rise (GMFR) in titer for each vaccination group across HAI titers for each 2023-24 influenza vaccine antigen 
Exploratory Outcome Measures:
 
 ii. The percent seroconversion and seroprotective titer, the geometric mean titer (GMT), and geometric mean fold rise (GMFR) in titer for each vaccination group across MN titers for each 2023-24 influenza vaccine antigen iii. GMT for SARS-CoV-2 binding antibody titer and viral neutralization titer (for a subset of samples) pre- and post-vaccination with mRNA COVID-19 vaccine iv. GMT and geometric mean fold change in HAI or MN titers at baseline, post-vaccination, mid-season, and post-season against 2023-24 circulating influenza virus and influenza vaccine antigens

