8.2 Analysis Plan of Year 2 Component D

HAI antibody titers will be compared between groups receiving the mRNA COVID-19 and cclIV4 influenza vaccines concomitantly or sequentially for each of the four influenza vaccine strains contained in the respective vaccines for that season as well as circulating influenza viruses and SARS-CoV-2 variants. Specifically, we will assess the following objectives:

Primary Objective 1a: Compare the proportion of participants in each vaccination group with a seroprotective HAI titer ($\geq 1:40$) pre- and post-cclIV4 immunization for each cclIV4 antigen. These proportions will be compared between vaccination groups using an exact Mantel-Haenszel statistic.

Primary Objective 1b: Compare the proportion of participants in each vaccination group achieving seroconversion following cclIV4 (an HAI titer $\geq 1:40$ following cclIV4 immunization if the baseline titer is $< 1:10$ or a four-fold rise in HAI titer if the baseline titer is $> 1:10$) for each cclIV4 antigen. These proportions will be compared between vaccination groups using an exact Mantel-Haenszel statistic.

Primary Objective 1c: Compare the GMT for each cclIV4 antigen and circulating influenza viruses pre- and post-cclIV4 immunization in each vaccination group. GMT will be compared between vaccination groups using a regression model.

Primary Objective 1d: Compare the GMFR in HAI titer for each vaccination group. GMFR will be compared between vaccination groups using a mixed effects regression model with a random intercept.

Exploratory objectives will be assessed using exact Mantel-Haenszel statistics to compare proportions between vaccination groups, regression models to compare GMT, and mixed effects regression models to compare GMFR. Tables will be provided summarizing counts and proportions for categorical outcomes or summary statistics and confidence intervals for

continuous outcomes. The statistical analysis of each exploratory objective will be fully described in the statistical analysis plan (SAP).

HAI titers will be log transformed prior to analysis and back transformed to estimate GMT and GMFR. The same analysis plan for HAI titers will be repeated for MN titers.

Data analysis will be performed using SAS version 9.4 software (SAS Institute Inc., Cary, NC) or R software (R Core Team, Vienna, Austria).

REFERENCES

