### 3 STUDY ENDPOINTS

#### 3.1 Primary

- i. Proportion of participants in each vaccination group with a seroprotective HAI (in a subset of samples) titer ( $\geq 1:40$ ) pre- and post-cclIV4 immunization for each 2023-24 influenza vaccine antigen
- ii. Proportion of participants in each vaccination group achieving HAI seroconversion (a titer  $\geq 1:40$  following cclIV4 if the baseline titer is  $< 1:10$  or a four-fold rise in titer if the baseline titer is  $> 1:10$ ) following cclIV4 vaccination for each 2023-24 influenza vaccine antigen
- iii. HAI GMT for each 2023-24 influenza vaccine antigen pre- and post-cclIV4 in each vaccination group
- iv. GMFR in HAI titers for each 2023-24 influenza vaccine antigen in each vaccination group

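### Sixteen primary HAI tests are each run at two-sided 0.05, with no lead endpoint, correction or rule for combining them

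*SAP*

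**What the plan says.** SAP 9.1 gives a null hypothesis, an alternative and P values for each of four primary endpoints, and sets one error rate for all of them: "All endpoints will be assessed with two-sided tests and alpha set to 0.05".

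The endpoints are per antigen. SAP 3.1 lists, for example, "GMFR in HAI titers for each 2023-24 influenza vaccine antigen in each vaccination group". Protocol 8.2 makes the comparison "for each of the four influenza vaccine strains contained in the respective vaccines for that season". The protocol summary lists the four measures side by side as primary outcomes, with none placed first: "The percent seroconversion and seroprotective titer, the geometric mean titer (GMT), and geometric mean fold rise (GMFR) in titer for each vaccination group".

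The tested contrast is concomitant against influenza-first: "Geometric mean fold rise will be compared between group i (concomitant administration) and ii (influenza administered first"). Two endpoints are also tested at baseline; for GMT, "GMTs before and 28-42 days after immunization will be compared between group i (concomitant administration) and ii (influenza administered first").

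The protocol and SAP disagree on the extent of the GMT comparison. Protocol 8.2, objective 1c, covers each vaccine "antigen and circulating influenza viruses pre- and" post-vaccination. Protocol 4.1 and SAP 3.1 confine the primary GMT to vaccine antigens, and protocol 4.2 and SAP EO5 treat circulating viruses as exploratory.

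On the model, SAP 7.1 promises a fixed site effect in every primary analysis, but SAP 9.1 assigns GMT a GEE that accounts for site clustering.

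**The concern.** The primary objective asks one scientific question: is the HAI response to ccIIV4 different when the mRNA vaccine is given on the same day? The plan answers it with 16 P values and does not say how they combine. The 5% rate then belongs to each test and not to the answer. If one or two of the 16 fall below 0.05, nothing in the plan stops them from being reported as a primary finding, and nothing tells a reader how often that would happen by chance. A choice of deciding endpoint made after the results are known would not be credible.

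The cost of a false signal is practical. An apparent lower response with same-day vaccination could count against a schedule that current guidance permits.

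**Working it through.** The documents state no familywise error, power or sample-size figure, so there is none to reproduce.

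**Inputs from the documents**
- Two-sided alpha of 0.05 per test; one contrast, group i v group ii (SAP 9.1).
- Four primary endpoints (SAP 3.1) and four antigens (protocol 8.2).
- Planned sizes (protocol summary): adults 300 v 150, children 100 v 50, hence 400 v 200 if pooled.
- Four sites (protocol summary) or seven (SAP 7.1).

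**Count**
- Post-vaccination: 4 endpoints x 4 antigens = 16 tests.
- Endpoints i and iii before vaccination: 2 x 4 = 8 more, 24 in all.
- The SAP does not say whether the age groups are pooled. Separate analyses would give 2 x 16 = 32 post-vaccination tests.

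**Reference values if tests were independent**
- 16 tests: 1 - 0.95^16 = 56.0%.
- Four tests (one endpoint, four antigens): 1 - 0.95^4 = 18.5%.
- 24 tests: 1 - 0.95^24 = 70.8%.

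The 16 tests are correlated, so 56% is too high for this plan.

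**Simulation with no true difference**

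Assumed: baseline SD 1.6 log2, SD of the rise 1.4 log2, baseline-rise correlation -0.3 to -0.5, between-antigen correlation 0 to 0.7. Titers were put in doubling dilutions, all four endpoints were derived, and simple z tests without site adjustment were used, with 3,000 trials per scenario.

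| Event among the 16 tests | Range |
|---|---|
| At least one P < 0.05, either direction | 35-47% |
| At least one P < 0.05 with concomitant lower | 17-26% |

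With between-antigen correlation limited to 0.2-0.7, the upper ends are 46% and 25%. The 300 v 150 and 400 v 200 results were close, so the size does not depend on pooling the age groups.

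A wider sensitivity check drew 16 correlated z statistics, with correlation 0 to 1 between endpoints and 0 to 0.7 between antigens. It gave 13-56% in either direction. Perfect correlation throughout would give 5%.

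**Does a correction work with the planned GMT model?**

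Null simulation of four antigens: SD 1.6 log2, antigen correlation 0.4, 300 v 150 and 400 v 200, 4,000 trials each. The GEE used an independence working correlation, an ordinary sandwich variance and a normal reference; these details are assumed because SAP 9.1 does not give them.

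| GMT analysis | One test at 0.05 | Any of four at 0.0125 (first Holm step) |
|---|---|---|
| GEE, 4 site clusters | 19% | 38% |
| GEE, 7 site clusters | 12% | 19-20% |
| Linear regression, fixed site effects | 5% | 4-5% |

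The sandwich variance rests on four or seven independent units, so it is too small on average. Holm alone would therefore not restore 5%.

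**Power cost of Holm**

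Take an effect with 80% power at two-sided 0.05: 1.960 + 0.842 = 2.802. At 0.0125 the critical value is 2.498. Power if only one antigen is affected: Phi(2.802 - 2.498) = Phi(0.304) = 0.62.

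**The case against.** The strongest reply is that the objective is worded as determining titers, in a Phase IV study of licensed or authorized vaccines, with results given antigen by antigen. On that view the P values are descriptive and familywise control is a matter of judgement. Part of this stands: the documents set no success criterion. But SAP 9.1 writes formal hypotheses with an alpha, and protocol 8.2 sets out to compare the groups on all four measures. A plan that tests formally should say how the tests are to be read.

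Three stronger readings are tempting, and the documents do not support them.
- A reader might infer a chance of about 40% of falsely finding interference. The tests are two-sided, and that figure includes false findings of a higher response with concomitant vaccination. The interference direction carries roughly half.
- A reader might infer that any one significant result decides the objective. No such rule is written; the defect is that no rule is written at all.
- A reader might infer from objective 1c that the primary family has no fixed size. Only that phrase in protocol 8.2 points that way. Protocol 4.1 and SAP 3.1 limit primary GMT to vaccine antigens. It is a wording conflict.

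It is also fair that the simulation of the 16 tests does not use the SAP's models, and that its spread and correlations are assumed. The figures are a range under assumptions and do not measure this trial's error rate. The GEE check suggests that the planned GMT analysis would do worse than simple tests. Finally, nothing in the documents ranks GMT above seroconversion, so the choice of lead is the sponsor's.

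**Conclusion.** The concern holds. Sixteen post-vaccination primary tests are each run at two-sided 0.05, and nothing links them to one conclusion. Under the assumptions above, at least one false difference in either direction has a chance of about 35-47%. A false interference signal has a chance of about 17-26%, roughly 7 to 10 times the 2.5% that one two-sided test allows in that direction. The count and the missing rule come straight from the documents; the percentages depend on correlations they do not give.

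This should be fixed. It does not invalidate the design or the data. It leaves the error rate of the primary conclusion undefined.

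**What to change.** Make these changes before results are seen.

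1. In SAP 9.1 and protocol 8.2, name one deciding primary endpoint, for example the post-vaccination HAI GMT ratio of group i to group ii. Test it on the four vaccine antigens with Holm at an overall two-sided 5%. State whether the age groups are pooled, since the family is four tests only if they are.
2. Analyse that endpoint by linear regression of log2 titer with fixed site effects, as SAP 7.1 already provides, and remove the site-clustered GEE for GMT.
3. Report the other three endpoints as supportive with unadjusted 95% confidence intervals. Show unadjusted intervals for the lead endpoint too, so that a real reduction on one antigen is not hidden.
4. As a minor separate point, remove circulating viruses from protocol 8.2 objective 1c so that it agrees with protocol 4.1 and 4.2 and SAP EO5.

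The cost is wording and one model specification, with no change to visits, samples or assays. The statistical price is power: an effect with 80% power at 0.05 has about 62% at the first Holm step if only one antigen is affected. The 80% is illustrative, since the documents contain no power calculation.

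### Seroprotection and seroconversion: the SAP names a titer ratio that its logistic model cannot give, and leaves the effect estimate for the difference in H0 unspecified

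*SAP*

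**What the plan says.** SAP 9.1 compares group i (concomitant) with group ii (influenza vaccine first) on four primary HAI endpoints. On error rate it says "All endpoints will be assessed with two-sided tests and alpha set to 0.05".

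- **Endpoints i and ii.** H0 is written as "Simultaneous group – Sequential group = 0", that is pi1 - pi2 = 0, with pi the seroprotection or seroconversion rate. The analysis sentence is the same under both: "P values and confidence intervals for the geometric mean titer ratio will be estimated using a logistic regression adjusted for site".
- **Endpoint iii (GMT).** "P values and confidence intervals for the geometric mean titer ratio will be estimated using a generalized estimating equation linear regression accounting for site clustering". Here a titer ratio is the right quantity.
- **Endpoint iv (fold rise).** "P values and confidence intervals for the geometric mean titer ratio will be estimated using a linear regression adjusted for site". The quantity should be a ratio of GMFRs, but the same phrase appears.

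SAP section 10 defines seroprotection and seroconversion as binary, and GMT as the anti-log of the mean log titer. SAP 7.1 puts a fixed site effect in every primary analysis.

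For the same two endpoints, Protocol 8.2 (Primary Objectives 1a and 1b) says: "These proportions will be compared between vaccination groups using an exact Mantel-Haenszel statistic".

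SAP 9.2 (Serology) applies the primary methods to the microneutralization, SARS-CoV-2 and circulating-virus objectives.

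**The concern.** The hypothesis concerns a difference in proportions, the model estimates an odds ratio, and the text promises a titer ratio. These are three different quantities. Striking out the wrong words does not reveal which measure was meant: the model points to an odds ratio, H0 to a difference, and the protocol to a Mantel-Haenszel analysis for which it names no effect measure. By contrast, SAP 9.2 (Safety) does specify a difference in proportions with a 95% CI, so these two primary endpoints are less fully specified than the safety endpoints.

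At stake is the reported effect and interval for two of the four primary endpoints. With four vaccine antigens, that is at least 2 x 4 = 8 comparisons. The gap also reaches the binary exploratory serology endpoints: seroprotection and seroconversion under EO1 (microneutralization) and EO5 (circulating influenza viruses). The trial is open-label, which is a further reason to fix the measure before results are seen.

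**Working it through.** The documents state no expected rates, effect size, SD or sample-size calculation, so there is no plan figure to reproduce. All rates and SDs below are assumptions. The planned numbers are from the Protocol Summary: 300 adults and 100 children in group i, 150 adults and 50 children in group ii.

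**1. Is a GMT ratio of 1 the same null as pi1 = pi2?** Take log2 titers as normal with the cut at 1:40, so pi = Phi((mean - cut)/SD). Let group ii have mean 1.0 above the cut and SD 1.0: pi2 = Phi(1.0) = 84.1%.
- Group i mean +1.5, SD 1.5: pi1 = Phi(1.0) = 84.1%, difference 0, but GMT ratio 2^0.5 = 1.41.
- Group i mean +1.0, SD 1.5: GMT ratio 2^0 = 1.00, but pi1 = Phi(0.667) = 74.8%, difference -9.4 points.

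So the named estimate is not a restatement of H0.

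**2. What does an odds ratio say about the difference?** pi1 = OR x odds2 / (1 + OR x odds2), with odds2 = pi2/(1 - pi2). For OR = 0.5:

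| Control rate | Odds | pi1 | Difference (points) |
|---|---|---|---|
| 50% | 1 | 0.5/1.5 = 33.3% | -16.7 |
| 80% | 4 | 2/3 = 66.7% | -13.3 |
| 95% | 19 | 9.5/10.5 = 90.5% | -4.5 |
| 99% | 99 | 49.5/50.5 = 98.0% | -1.0 |

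Conversely, a fixed -10-point difference with 300 vs 150 adults (Wald 95% CIs):

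| Group ii rate | Difference, 95% CI | OR, 95% CI |
|---|---|---|
| 50% | -0.197 to -0.003 | 0.67 (0.45 to 0.99) |
| 80% | -0.182 to -0.018 | 0.58 (0.37 to 0.93) |
| 90% | -0.166 to -0.034 | 0.44 (0.24 to 0.81) |

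**3. Is the logistic test itself sound?** Within a site, OR = 1 holds exactly when pi1 = pi2. In simulation (600 participants split 2:1 over four sites, control rates 60%, 70%, 75% and 80%, 2,000 runs with pi1 = pi2), the site-adjusted logistic P value rejected in 5.4% of runs. The Monte Carlo standard error is sqrt(0.05 x 0.95/2000) = 0.5 points, so this agrees with 5%. With a true difference of -0.10, the adjusted OR averaged 0.62. Averaging predicted risks over the sample gave a difference of -0.102, so one standardisation step recovers the H0 scale.

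**4. Can the model break down?** If group ii has no non-responders for an antigen, the odds ratio is infinite or not estimable. That chance is p^n, with n = 200 (adults and children) or 150 (adults):

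| True rate | n = 200 | n = 150 |
|---|---|---|
| 99% | 13% | 22% |
| 98% | 1.8% | 4.8% |
| 97% | 0.2% | 1.0% |
| 95% | below 0.05% | below 0.05% |

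The protocol plans HAI in a subset of samples; a smaller n would raise these figures.

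**5. Can a Mantel-Haenszel CI simply be paired with the exact test?** Simulation: 400 vs 200 in six strata (four adult and two child sites), 4,000 runs, Sato variance for the CI. With equal true rates of 99%, the CI excluded 0 in about 8% of runs, the exact test rejected in about 3%, and the two disagreed in about 8%. At 90% vs 95% they rejected in about 64% and 54% of runs and disagreed in about 10%.

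**The case against.** The strongest reply is that this is a pasted phrase. The same words stand under all four endpoints, including the fold rise, and fit only endpoint iii. For endpoints i and ii the SAP still fixes the outcome, the contrast, the hypotheses, alpha, sidedness, the model and the site adjustment. All of that stands, and copying is the likely explanation. It does not supply the missing measure, though: with the phrase removed, the scale of the estimate and CI is still not stated.

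A reader might infer that H0 for these endpoints cannot be tested. The documents do not support that: the named model yields a valid P value for pi1 = pi2, as step 3 shows.

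A reader might also infer that the model is likely to fail at the seroprotection ceiling. That depends on rates the documents do not give. The risk is appreciable at 99%, small at 98% and negligible at 95% for the planned numbers. The argument also concerns seroprotection; nothing here suggests that seroconversion would sit near a ceiling.

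Finally, choosing Mantel-Haenszel over logistic regression is partly a matter of preference. That is fair, and step 5 shows that a Mantel-Haenszel interval paired with an exact P value has problems of its own.

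**Conclusion.** The point holds as a defect of specification. For two of the four primary endpoints, the estimate named in SAP 9.1 cannot come from the model named, is not the parameter in H0, and rests on a method that differs from protocol 8.2. The hypothesis test survives; the effect measure and its interval do not. The same halving of the odds can mean a difference anywhere from -16.7 to -1.0 points as the assumed control rate runs from 50% to 99%, so the choice of scale would change how a result reads. The breakdown risk is a secondary matter, conditional on very high response rates. The correction is worth making before analysis, but it does not call the design or the test into question.

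**What to change.** In SAP 9.1, endpoints i and ii:

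1. Delete the reference to a geometric mean titer ratio. State that the estimate is pi1 - pi2 with its 95% CI, obtained as a standardised (marginal) risk difference from a logistic regression with terms for group, site and age group. Randomization is stratified by site and age group (SAP 4.3), while the current model adjusts for site only.
2. Take the P value and CI from one coherent method, so that they cannot contradict each other.
3. Name a fallback for antigens where an arm has few or no non-responders, for example a score-based or exact stratified method that supplies both P value and CI. Set its trigger in advance.
4. Reconcile with protocol 8.2, by amending it or by recording the departure and the reason in the SAP.
5. State that the same wording governs the binary endpoints under EO1 and EO5. In endpoint iv, call the quantity a GMFR ratio.

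Keeping the odds ratio would also be coherent if H0 were restated as OR = 1, but the difference matches the stated hypotheses and the safety analysis. The cost is a few sentences and standard SAS or R procedures, plus a decision on the fallback trigger. No new data are needed.

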3.2 Protocol Background and Rationale

Current guidance concerning administration of U.S.-approved or -authorized COVID-19 vaccines indicates that these vaccines may be given with influenza vaccines.¹

In accordance with general best practices, routine administration of all age-appropriate doses of vaccines concomitantly is recommended for children, adolescents, and adults for whom no specific contraindications exist at the time of the healthcare visit. Providers should be aware of the potential for increased reactogenicity with concomitant administration and should consult updated CDC guidance as more information becomes available.

Extensive experience with non-COVID-19 vaccines has demonstrated that immunogenicity and adverse event profiles are generally similar when vaccines are administered concomitantly as when they are administered alone.

Studies that compared coadministration of COVID-19 vaccines and seasonal influenza vaccines with separate administration of these vaccines found similar levels of immunogenicity and similar or slightly higher reactogenicity;²⁻⁴ no specific safety concerns were identified.

During the 2023-2024 influenza season, CDC plans a randomized influenza vaccine immunogenicity study to compare immune responses to concomitant vs sequential administration of licensed or authorized vaccines for COVID-19 and influenza in select age groups. For future seasons, immunogenicity studies may enroll different age groups each season depending on the vaccines to be compared. To study immune responses to vaccination, each study site will recruit and enroll up to 250 participants who are eligible to receive specific influenza and COVID-19 vaccines and for whom the vaccines are recommended. Study sites will implement common protocols developed in collaboration with CDC. Data will be combined across sites so that all sites will contribute to a total anticipated sample size of 800 participants for comparisons of immune responses by vaccine administration schedule. Investigators will collect, process, store, and ship sera, plasma, and PBMC specimens to a designated CDC laboratory for testing. Some additional specimen testing may be performed by a CDC-approved site.

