## 7.1 Multicenter Studies

There are 7 sites participating in the study. Data will be pooled across investigational sites for analysis purposes. A fixed site effect will be included in all analyses of the primary objective.

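### Protocol and SAP name different tests for the two binary primary endpoints, and the SAP's logistic regression has no stated test statistic and no rule for an arm with no failures

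*SAP*

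**What the plan says.** Protocol 8.2 gives the same sentence under Primary Objectives 1a (HAI titer of at least 1:40) and 1b (seroconversion): "These proportions will be compared between vaccination groups using an exact Mantel-Haenszel statistic". It names no stratifying variable. It leaves the full description of the exploratory analyses to the SAP, but makes no such deferral for the primary ones.

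SAP 9.1 compares group i with group ii. For both endpoints i and ii it states that P values and confidence intervals "will be estimated using a logistic regression adjusted for site". It mentions no Wald, likelihood-ratio, score, exact or penalised version and no fallback for a zero cell. The general rule is "All endpoints will be assessed with two-sided tests and alpha set to 0.05". SAP 7.1 adds "A fixed site effect will be included in all analyses of the primary objective". SAP 9.2 carries the primary methods over to microneutralization and circulating-virus titers, so the conflict extends to those proportions.

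Two related mismatches bear on the repair:

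- **Sites.** SAP 7.1 says "There are 7 sites participating in the study", while the protocol summary lists four. Both documents stratify randomisation by age group and site (protocol 5.4.2, SAP 4.3).
- **GMFR.** Protocol 8.2 says "GMFR will be compared between vaccination groups using a mixed effects regression model with a random intercept". SAP 9.1 endpoint iv uses a linear regression adjusted for site.

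**The concern.** Two different primary tests are on file for the same endpoints, with no rule on which one governs. At mid-range proportions this would be untidy but harmless, because the tests agree. Seroprotection after vaccination may not be mid-range. The participants are healthy, most antigens will have been met before, and the threshold is fixed at 1:40. If nearly everyone in an arm passes it, the number of failures in that arm can be very small or zero.

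That is where a logistic model depends on details the SAP omits. With no failures in one arm, the maximum-likelihood log odds ratio is infinite. Its standard error grows faster than the estimate, so the Wald statistic falls towards zero and the P value rises towards 1. A real shortfall in the concomitant arm could then be reported as clearly non-significant, while the protocol's test on the same data rejects. The sequential arm is half the size of the concomitant arm and so is the likelier one to have no failures. If coadministration lowers the response, it is also the arm nearer the ceiling.

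**Working it through.** The documents contain no power calculation, effect size or expected rate, so there is no figure of the plan's own to reproduce. The check compares the two named methods under stated assumptions.

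**Inputs**

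- Allocation, from the protocol summary: group i has 300 adults and 100 children, group ii has 150 adults and 50 children. Pooled, that is 400 v 200.
- Analysed number: 90% of these is assumed, giving 0.9 × 400 = 360 and 0.9 × 200 = 180. The documents give no attrition rate.
- Sites: four equal strata of 90 v 45. Equal size is a simplification, since only two sites enrol children.
- Seroprotection rates: assumed throughout.
- Level: two-sided 0.05, from SAP 9.1.

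**Step 1. How often does the sequential arm have no failures?** With true rate p and n = 180, the probability is p^n.

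- p = 0.99: 0.99^180 = 0.16
- p = 0.995: 0.995^180 = 0.41

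**Step 2. What does each method do with such a data set?** Take 18 failures among 360 (5%) and none among 180, ignoring site. Given 18 failures in all, the exact probability that every one falls in the concomitant arm is the product of (360 − i)/(540 − i) for i = 0 to 17, which is about 0.0006. The exact test rejects clearly. The Wald test from the logistic fit cannot reject, for the reason given above.

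**Step 3. Power over repeated trials.** Simulated, 2,000 to 3,000 replicates per case where recorded. The exact test is the conditional stratified test (convolved hypergeometric distributions). The logistic model has fixed site effects.

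| Concomitant v sequential | Exact Mantel-Haenszel | Logistic, Wald |
|---|---|---|
| 95% v 100% | 99% | 0% |
| 96% v 99.5% | 71% | 21% |
| 95% v 99% | 70% | 47% |
| 93% v 98% | 71% | 67% |
| 90% v 97% | 88% | 87% |
| 99% v 95% (reverse direction) | 78% | 76% |
| 60% v 72% | 79% | 80% |

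**Step 4. Type I error with 99% in both arms.** Across repeated runs of the same design:

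- exact: 2.3% to 2.6%
- Wald: 1.0% to 1.1%
- likelihood-ratio: 7.7% to 8.7%
- score test of the same model (essentially the Cochran-Mantel-Haenszel test): 3.8% to 4.2%

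The score test also keeps its power: 72% at 95% v 99%, and 76% at 96% v 99.5%.

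**Step 5. Sensitivity to the design assumptions.**

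- Adults only, full allocation, 300 v 150 at four sites: exact against Wald is 59% v 28% at 95% v 99%, 79% v 25% at 95% v 99.5%, and 97% v 0% at 95% v 100%.
- Seven sites instead of four changes these by about 2 points at most.
- Adults at 50% v 60%: exact 51%, Wald 52%, so no loss.
- Children only, 100 v 50 at two sites: at 95% v 100% the Wald test again has no power, but the exact test has only 8%. There the sample size is the main limit, not the choice of test.

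**The case against.** The strongest reply is that the SAP does not specify the version that fails. It says logistic regression adjusted for site and no more. Maximum likelihood with a Wald test is the usual default, not the SAP's wording. The score test of the same model does not break down, and an exact or penalised fit would also cope. This stands. A reader might infer that the SAP's analysis itself loses most of its power or its error control. The documents do not support that, because they name no statistic. Nor does any one version have both faults: Wald is conservative and loses power, while likelihood-ratio keeps power and exceeds 5%.

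Second, the loss is local. Most of the power goes only when the sequential arm is at about 99.5% or higher. At 95% v 99% the Wald test keeps about two thirds of the exact test's power (47/70 = 0.67). No rate in the documents says that any antigen will be in that range. This also stands.

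Third, a reader might extend the numerical harm to seroconversion, or to the pre-vaccination comparison of seroprotection. No near-ceiling case is made for either, and at mid-range rates the methods agree.

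Fourth, GMT and GMFR are also primary for each antigen and do not suffer from separation. A real drop in response would therefore not rest on the seroprotection test alone. True, but each endpoint is reported with its own P value, and a misleading one remains misleading.

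Finally, both documents describe the primary HAI endpoints partly as measured in a subset of samples, so 360 v 180 may not be the analysed number. Smaller numbers make an arm without failures more likely.

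None of this removes the conflict between the two documents, which needs no assumption.

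**Conclusion.** The point holds as a conflict between protocol and SAP on the primary test for endpoints i and ii, together with an under-specified replacement. The conflict is certain. Its numerical consequence is conditional.

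Under ordinary maximum likelihood with a Wald test and 360 v 180 analysed, power falls from about 70% to 47% at 95% v 99%, from about 71% to 21% at 96% v 99.5%, and to zero when an arm has no failures. The fall is about 4 points at 93% v 98% and negligible at 90% v 97% or at mid-range rates. Under a likelihood-ratio test power is kept, but two-sided error is about 8% at 99% in both arms.

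These results rest on assumed seroprotection rates, 90% retention and equal sites, and they concern mainly endpoint i after vaccination. Nothing in the documents suggests that anyone means to choose between the tests after seeing results. They simply leave that choice open, in an open-label trial. The GMFR mismatch is a separate inconsistency, and no size is claimed for it.

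**What to change.** In SAP 9.1, endpoints i and ii, restore the protocol's exact Mantel-Haenszel test as the source of the primary P value, and keep the site-adjusted logistic regression as supportive. State the strata in both documents. They should be the actual randomisation strata, age group and site, once the four sites of the protocol and the seven of SAP 7.1 have been reconciled. Four site strata alone would not match the randomisation.

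Alternatively, amend both documents to one named test that survives separation, such as the score (Cochran-Mantel-Haenszel) test or an exact or Firth logistic regression, and say what will be reported when an arm has no failures.

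Separately, state one GMFR model in both documents. If the random intercept is kept, say which unit it belongs to.

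The cost is a few lines of SAP text and code. The exact test is slightly conservative, with about 1 to 2 points less power at mid-range rates. The change should be made before the titers are compared between groups.
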